STUDY PROTOCOL

Use of transcutaneous electrical nerve stimulation (TENS) for the recovery of oral function after orthognathic surgery

NCT ID not yet assigned

05/11/2020

ABSTRACT:

Oral functions of patients are markedly diminished immediately after orthognathic surgery, and novel approaches are needed to accelerate their recovery. The aim of this study will be to examine the usefulness of weekly applications of transcutaneous electrical nerve stimulation (TENS) for this purpose, based on evidence of its effectiveness in other types of patients with muscle alterations. Maximum jaw opening, bite force, pain, and facial inflammation will be compared between patients receiving TENS and those receiving sham-TENS for 30 min at baseline and weekly over a four-week period after orthognathic surgery and will be also compared between before and after each procedure.

MATERIAL

The sample will be made up of a sufficient number of patients according to the calculation of the sample size who will undergo bimaxillary surgery or mandibular surgery divided between experimental (TENS group) and control groups (sham-TENS).

Participants will be selected by non-probabilistic sampling of consecutive patients until the estimated sample size is reached. All patients have a skeletal and facial deformity amenable to surgery after a pre-surgical orthodontic period, and they will have to signed their informed consent after receiving an information sheet on the study.

This study was approved by the ethics committee of the hospital (San Carlos Hospital, Madrid, Spain).

Inclusion criterion:

- programing of bimaxillary or mandibular orthognathic surgery by the same surgeon in order to avoid inter-operator variability.
- no surgery for temporomandibular disorders or more complex syndromes,
- no presence of muscle or nervous disorders or receipt of medication for such disorders

Exclusion criterion:

- the impossibility to attend follow-up appointments
- the refusal of informed consent.

The sample size will be estimated to obtain a statistical power of 80% with an alpha error of 0.05 and 95% confidence interval to detect a difference in jaw opening ≥ 2.5 mm.

Patients will be randomly assigned to the experimental group for TENS application or the control group for sham-TENS and will be blinded to their group assignation, as was the researcher responsible for data analyses (single-blind randomized clinical trial).

METHOD

TENS procedure

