An Enraf Nonius® S82 model TENS device will be used, with a maximum frequency of 220 Hz and an intensity range of 0 to 99.5 mA.

TENS electrodes will be placed bilaterally on mandibular elevator muscles, on the superficial masseter muscle above the gonial angle, and bilaterally on the anterior temporal muscle, following the manufacturer's instructions. The device will be applied in an identical manner to all patients in both groups and kept in position for the same time period (30 min); however, the device will be not switched on for the control group.

The stimulation intensity will be adjusted for those in the experimental group to the maximum that did not cause discomfort or areas of contraction, maintaining this stimulation intensity and frequency throughout the 30-min session.

Each participant will experience a weekly TENS or sham-TENS session on the same day of the week during a four-week period; appointments will be scheduled so as to minimize any possible interaction among study participants.

Study variables

Data will be gathered from all patients on jaw opening, bite force, inflammation, and pain before surgery and at 7, 14, 21, and 28 days post-surgery, conducting measurements both before and after the TENS/sham-TENS session.

Maximum Jaw Opening will be evaluated with patients seated vertically upright in the dental chair, using a digital dental caliber (Model R 100110, Mestra®) to measure the maximum opening from the incisal margin of upper central incisors to the incisal margin of lower incisors, adding the amount (in mm) of overbite or subtracting the amount (in mm) of open bite in occlusion.

Bite force will be measured using Dental Prescale Fuji® film, which is formed by microcapsules that generate a chemical reaction under pressure, staining the contact area with a color density corresponding to the pressure applied.

A sheet of the film will be placed between the occlusal surfaces of the two arches, and the patient will be asked to bite as strongly as possible for 5 sec. This procedure will be repeated three times, selecting the sheet with the best-defined tooth print to be photographed with a Canon® EOS 500 camera (RAW format, F32, and annular Flash) at the minimum distance permitted by the 75-macro lens.

The image will be processed in a Mac® computer to obtain the color value according to the Cie L*a*b* (CIELAB) scale, which gives the color a numerical value.

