### *Statistical analysis*

Descriptive statistics will be conducted to calculate distributions, frequencies, means and standard deviations for sex, malocclusion, and the results for maximum opening, bite force, inflammation, and pain in each group (experimental and control).

The Kolmogorov-Smirnov test will be applied to check the normality of variable distributions and Levene's test to check the equality of variances.

The Student's t-test will be employed to evaluate the difference in each measurement between experimental and control groups.

The paired Student's t-test will be used to compare measurements before and after TENS/sham-TENS in the same patient.

The GLM repeated-measures procedure will be applied to analyze the results for each group over time.

SPSS 22.0 ® for Windows will be used for statistical analysis

P≤0.05 was considered significant in all tests.

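### The SAP's only over-time analysis drops every patient with a missed visit, and it does not say which within-subject test will be read

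*SAP*

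**What the plan says.** The SAP (Statistical analysis) lists three inferential methods, all to be run in SPSS 22.0:

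- a Student's t-test between arms for each measurement;
- a paired t-test within patient around each session;
- for the time course, "The GLM repeated-measures procedure will be applied to analyze the results for each group over time".

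The significance rule is "P≤0.05 was considered significant in all tests". The assumption checks named are Kolmogorov-Smirnov for normality and Levene for equal variances.

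The Protocol (Study variables) schedules all outcomes "before surgery and at 7, 14, 21, and 28 days post-surgery", "conducting measurements both before and after the TENS/sham-TENS session". Its exclusion criteria remove at entry patients who could not come to follow-up.

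The text available for review has no rule for missed visits, no list of the occasions that enter the GLM, no mention of sphericity, and no choice between univariate, corrected and multivariate tests. The Protocol states neither a sample size nor a standard deviation. It says only that there will be "a sufficient number of patients according to the calculation of the sample size", set "to detect a difference in jaw opening ≥ 2.5 mm".

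**The concern.** GLM repeated measures works on one row per patient and needs a value in every column entered. A patient who attends all but one weekly appointment contributes nothing to it. The handling of missed visits is therefore fixed by the chosen procedure, even though the SAP never states it.

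Two things are at stake. The first is information: visits that were attended and measured are discarded. The second is bias. After jaw surgery, attendance may depend on pain or on how well the patient is recovering. An analysis confined to perfect attenders then describes a selected group, and the selection may differ by arm.

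A separate and smaller gap concerns the choice of test. The procedure can give an uncorrected univariate F, epsilon-corrected versions and a multivariate test for time and for arm-by-time. Only the uncorrected F needs sphericity, meaning equal variances of all pairwise differences between occasions. One pre-surgery occasion followed by four weekly post-surgery occasions makes that doubtful. If the test is not named in advance, the one with too high a rejection rate may be the one reported.

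**Working it through.** **No stated figure to reproduce.** The documents give no N, SD or missed-visit rate. Everything below is illustration on stated assumptions.

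**1. Patients and visits lost to listwise deletion**

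Inputs:
- k = 5 scheduled occasions (Protocol, Study variables), or k = 4 if only post-surgery visits are entered or at risk of being missed;
- m = share of patients missing any given visit, assumed.

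Formulas:
- Complete patients, if misses are independent: (1 − m)^k.
- Bounds for the same m: 1 − km if no patient misses more than one visit, up to 1 − m if the same patients miss every visit.
- Share of attended visits discarded, under independence: 1 − (1 − m)^k / (1 − m) = 1 − (1 − m)^(k−1).

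| m | k | Complete, independent | Bounds | Attended visits discarded |
|---|---|---|---|---|
| 5% | 5 | 0.95^5 = 0.7738 | 0.75 to 0.95 | 1 − 0.95^4 = 0.185 |
| 10% | 5 | 0.90^5 = 0.5905 | 0.50 to 0.90 | 1 − 0.90^4 = 0.344 |
| 5% | 4 | 0.95^4 = 0.8145 | 0.80 to 0.95 | 1 − 0.95^3 = 0.143 |
| 10% | 4 | 0.90^4 = 0.6561 | 0.60 to 0.90 | 1 − 0.90^3 = 0.271 |

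Over a wider range, 2% missed per visit leaves 90% complete (k = 5) or 92% (k = 4), and 15% leaves 44% or 52%.

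**2. Rejection rate of the arm-by-time test under the null**

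Assumed: 20 per arm, normal data, no missing values, nominal 0.05, 10,000 simulated trials per row. The Monte Carlo standard error is about √(0.05 × 0.95 / 10,000) = 0.002. Epsilon is 1 under sphericity and falls as the departure grows.

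| k | Covariance | Epsilon | Uncorrected F | Greenhouse-Geisser | Multivariate |
|---|---|---|---|---|---|
| 4 | Compound symmetry 0.5 | 1.00 | 0.050 | 0.045 | 0.050 |
| 4 | AR(1) 0.5 | 0.86 | 0.063 | 0.051 | 0.053 |
| 4 | AR(1) 0.8 | 0.72 | 0.067 | 0.048 | 0.049 |
| 4 | AR(1) 0.8, SD rising 1 to 2.5 | 0.60 | 0.078 | 0.050 | 0.045 |
| 5 | Compound symmetry 0.5 | 1.00 | 0.049 | 0.043 | 0.047 |
| 5 | AR(1) 0.5 | 0.81 | 0.057 | 0.041 | 0.048 |
| 5 | AR(1) 0.8 | 0.63 | 0.076 | 0.048 | 0.046 |
| 5 | AR(1) 0.8, SD rising 1 to 2.5 | 0.53 | 0.086 | 0.049 | 0.048 |

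With constant variance and AR(1) correlation, the uncorrected F rejects in 5.7% to 7.6% of null trials. The strongest departure tried, with rising variance over five occasions, gives 8.6%. The other two tests stay near 5% throughout. The test of time within a single arm behaves similarly: 5.6% to 8.8% uncorrected in the non-spherical cases.

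**3. Which analyses are touched**

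The Student's t-test at a visit uses everyone measured at that visit. The paired t-test needs only the two values from one session. Neither requires a full set of visits, so deletion in the GLM leaves both unchanged. The between-arm main effect in the GLM does not need sphericity either, although it does lose the incomplete patients.

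**The case against.** The strongest reply is that the loss may be small. Follow-up lasts 28 days, patients unable to attend are excluded at entry, and a patient who has had surgery probably has a pre-surgery value, so four occasions are the more realistic number at risk. Missed visits also tend to fall on the same patients; at the fully clustered bound, 5% missed per visit leaves 95% complete rather than 77%. All of this stands. It limits the size of the problem, but nothing in the plan rules missed visits out.

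A second reply is that the SAP does not commit to the uncorrected F. That also stands. A reader might infer that the over-time p-values will be too small. The documents do not support this, because they do not say which test will be read, and two of the three candidates hold their level.

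A third concerns power. A reader might start from an 80% design and apply Φ(√share × (1.960 + 0.842) − 1.960). With a share of 0.7738 this gives about 69%, and with 0.5905 about 58%. It would be wrong to call this the trial's power loss. The formula is for a two-sample contrast between arms, which the SAP gives to the Student's t-test, and deletion in the GLM does not touch that test. The 2.5 mm target is not tied to the GLM, and no N, SD or missed-visit rate is stated.

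Finally, a mixed model does not cure every form of missingness. If patients stay away because of pain that was never recorded, it can be biased too.

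**Conclusion.** The concern holds for the over-time analysis only. The named procedure will exclude any patient missing an entered occasion, which wastes recorded data and can bias the time-course result if attendance relates to recovery. Under independent misses at 5% or 10% per visit, about 77% or 59% of patients would remain over five occasions, or 81% or 66% over four. These shares rest on an assumed rate and on independence, and they would be higher if misses cluster within patients.

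The within-subject test is an unspecified choice. Understated p-values and a loss of power for the 2.5 mm between-arm difference are not shown. If the uncorrected F were the test read, its error rate would be about 6% to 8% at nominal 5% in most of the non-spherical settings tried, with 20 per arm assumed. The change is worth making because this is the plan's only longitudinal analysis and a better method is available in the same software.

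**What to change.** Replace GLM repeated measures with a linear mixed model (MIXED in SPSS) for each outcome:

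- all randomised patients, in their assigned arm, and all available post-surgery visits;
- arm, visit and arm-by-visit as fixed effects;
- as covariate, one named baseline value measured before the first TENS or sham session, and not also used as a response;
- a statement of which measurement at each visit, pre-session or post-session, is the response;
- an unstructured covariance across visits, with a prespecified simpler structure if it does not converge.

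Report the between-arm difference with its confidence interval at each visit. State that the model is valid when missingness depends on observed data, and report the number of missed visits by arm. If GLM is kept as a secondary display, prespecify the Greenhouse-Geisser corrected test and state how many patients it excludes.

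The cost is one paragraph of SAP text and slightly more analysis work in the same package, with no extra patients or visits. The downside is that the covariance may have to be simplified if the sample is small.
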